2.3.2 Secondary outcomes

The overarching rationale for selecting these secondary outcomes is capturing more holistic, broader effects of offering financial incentives on users' behaviours. There are three categories of secondary outcomes: PA, diet, and weight.

2.3.2.1 Secondary outcome - physical activity

We will focus on one secondary PA outcome to supplement the primary PA outcome, and it will also be collected via the wearable device:

Energy expenditure. Energy expenditure is defined as daily calories (kcal/day) burnt from physical activity. Since MVPA doesn't take into account lighter forms of physical activity (e.g. walking) and steps are only one specific form of activity, we included energy expenditure as a secondary outcome as a holistic measure of physical activity.

2.3.2.2 Secondary outcome - diet

We will supplement the four primary dietary outcomes two secondary outcomes:

Energy intake (kcal/day). Given the high prevalence of overweight and obesity and the role of energy intake in the aetiology of obesity, we will assess the impact of the scheme on participants' energy intake. ³²

Healthy eating score

We will derive a healthy eating score based on consumption of key food groups, macro- and micronutrients following the methodology by Scheelbeek et al. 2020³³ The rationale to include this score is twofold:

- First, this holistic measure enables us to better capture the combined effects of the 10 health challenges, each of which targets different food groups.
- Second, it allows us to capture the intervention impact on diet aspects that are not covered by the primary outcomes (e.g. salt) without unduly increasing the number of individual outcomes assessed by the study.
- The scheme allows us to holistically capture intervention effects on metrics that:
 - $\circ~$ are closely embedded in the ToC we proposed for dietary intake
 - are tied with at least one incentive
 - have been used in studies with similar contexts, which increases comparability of results and enables easier synthesis of evidence

³² Health Survey for England 2019. Available from:

https://digital.nhs.uk/data-and-information/publications/statistical/health-survey-for-england/2019#summary

³³ Scheelbeek P, Green R, Papier K, Knuppel A, Alae-Carew C, Balkwill A, Key TJ, Beral V, Dangour AD. Health impacts and environmental footprints of diets that meet the Eatwell Guide recommendations: analyses of multiple UK studies. BMJ open. 2020 Aug 1;10(8):e037554.

 are linked with a clear government dietary recommendations for healthy eating

Following Scheelbeek et al. 2020³⁴ we will score participants' diets measured with Intake24 using a dichotomous system to assess whether the diet meets each of the following criteria:

Metric	Criteria for point allocation	Following methodology by	
Fruit and vegetables (g/day)	≥ 400 g	Scheelbeek et al. 2020	
Red & processed meat (g/day)	≤ 70g	Scheelbeek et al. 2020	
Free sugars (g/day)	≤ 30 g	Scheelbeek et al. 2020	
Saturated fat (g/day)	For males \leq 30 g For females \leq 20 g	Scheelbeek et al. 2020	
Fibre (g/day)	≥ 30 g	Scheelbeek et al. 2020	
Total fat (g/day)	For males $\leq 97g$, $\leq 91g$, $\leq 89g$, respectively for age groups 18-64, 65-74, 75+ For females $\leq 78g$, $\leq 74g$, $\leq 72g$, respectively for age groups 18-64, 65-74, 75+	Scheelbeek et al. 2020	
Salt (g/day)	≤ 6 g	Scheelbeek et al. 2020	

Table 4. Intake24 Criteria

For each metric, participants will score 1 if their consumption meets the corresponding criteria for point allocation, and 0 if they don't. Since we will measure diets with 24 hours dietary recalls and recommendations for fish are expressed on a weekly basis, we decided to drop the metrics pertaining to (i) oily fish and (ii) other fish consumption, which were used in the original index by Scheelbeek et al. 2020.³⁵ Since there are 7 metrics in total, the value range of the score varies from 0 to 7 (0 = least healthy, 7 = most healthy).

2.3.2.3 Secondary outcome - weight

Although the financial incentive scheme is not a weight loss app, measuring weight is important to help assess whether this healthy eating and physical activity intervention could also help to reduce the prevalence of obesity or indeed to rule out potential unintended consequences on weight.

³⁴ Scheelbeek P, Green R, Papier K, Knuppel A, Alae-Carew C, Balkwill A, Key TJ, Beral V, Dangour AD. Health impacts and environmental footprints of diets that meet the Eatwell Guide recommendations: analyses of multiple UK studies. BMJ open. 2020 Aug 1;10(8):e037554.

³⁵ Scheelbeek P, Green R, Papier K, Knuppel A, Alae-Carew C, Balkwill A, Key TJ, Beral V, Dangour AD. Health impacts and environmental footprints of diets that meet the Eatwell Guide recommendations: analyses of multiple UK studies. BMJ open. 2020 Aug 1;10(8):e037554.

Participants will be asked to self-report their current weight at the baseline and each measurement timepoint. The app will encourage participants to weigh themselves when entering weight data.

2.3.3 Exploratory outcomes

The primary outcomes focus on participants' behaviours. To understand whether the financial incentive scheme affects participants' motivation to change behaviours as well as potential unintended consequences, we propose two types of exploratory outcomes.

2.3.3.1 Exploratory outcomes - Motivation to change

To understand whether the financial incentive scheme affects participants' motivation to change behaviours in PA and diet, we propose two exploratory outcomes to capture participants' motivation to change before and after the intervention. We will use a 5-point Likert scale (1=not at all confident/willing to 5=very confident/willing with 3 being neutral) for each question, and average across the two items:

[figure not shown]
- Motivation to change physical activity:
 - How willing are you to make changes in your physical activity habits in order to be healthier in the next 6 months?
 - How confident are you in making these changes to your physical activity habits in the next 6 months?
- Motivation to change diet:
 - How willing are you to make changes in your eating habits in order to be healthier in the next 6 months?
 - How confident are you in making these changes to your eating habits in the next 6 months?

We will collect these measures at baseline and m5, and examine the impact of offering incentives compared to not offering any incentives.

2.3.3.2 Exploratory outcomes - unintended consequences

We propose two exploratory outcomes to investigate the unintended effects of the interventions: **mental health, and sleep duration**.

First, as suggested by a recent meta-analysis, increased levels of physical activity and healthier diet might improve people's **mental health**. We propose to measure participants' well-being as an exploratory outcome to capture the potential effects of the interventions beyond physical health (positive or negative). Mental wellbeing will be collected at baseline and key collection points (m1, m3, m5) by prompting users via push notifications and in-app prompts to assess their mental health using the WHO-5 WHO-5 Well-being questionnaire to measure people's mental well-being. The WHO-5 is a simple and validated index consisting of five statements, which respondents rate (in relation to the past two weeks) according to the screenshots below.

For each statement, participants choose one of six frequencies and their answers will be coded into a numeric value (all of the time = 5, at no time = 0). The total raw score, ranging from 0 to 25, is multiplied by 4 to give the final score, with 0 representing the worst well-being and 100, the best.

Second, we will analyse effects on sleep duration (as measured by the duration of sleep (hour/day) by the wearable).³⁶ We use sleep duration as potential unintended consequence because physical activity could improve sleep quality in general³⁷, but it also could impair sleep quality if participants do vigorous physical activity within 1 hour before bedtime³⁸.

³⁶ HUL will prompt users to wear the device at nights, but as a secondary call-to action (i.e. prompt once in the app at key collection points (baseline, m1, m3, m5).

³⁷ Banno M, Harada Y, Taniguchi M, et al. Exercise can improve sleep quality: a systematic review and meta-analysis. PeerJ. 2018;6:e5172. Published 2018 Jul 11. doi:10.7717/peerj.5172

³⁸ Stutz J, Eiholzer R, Spengler CM. Effects of Evening Exercise on Sleep in Healthy Participants: A Systematic Review and Meta-Analysis. Sports Med. 2019 Feb:49(2):269-287. doi:

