- A. Control group: Access to the HeadUp app and the wearable tracker
- **B.** Intervention groups: On top of the HeadUp app and the wearable tracker participants will receive a financial incentive intervention for the entire duration of the trial with:
 - **B.1** low value incentives, i.e. low £ per point ratio
 - $\circ~$ **B.2** medium value incentives, i.e. medium £ per point ratio
 - **B.3** high value incentives, i.e. high £ per point ratio

A detailed description of the intervention and baselining logic is provided separately by HUL.

The primary outcomes consist of **2 physical activity outcomes** and **4 dietary outcomes**. The primary physical activity outcomes will be (i) moderate and vigorous physical activity (MVPA) in minutes per day and (ii) daily steps measured objectively through a wearable device. The primary dietary outcomes will be daily intake of (i) fruit and vegetables (g/day), (ii) fibre (g/day), (iii) saturated fat (% of food energy intake) and (iv) free sugars (% of food energy intake) measured through 24 hour dietary recalls. Secondary outcomes will be (i) daily energy expenditure as measured by the wearable, (ii) daily energy intake as measured by 24 hour dietary recalls (Intake24 surveys), (iii) a healthy eating score based on consumption of key food groups, macro- and micronutrients, and (iv) self-reported weight.

Exploratory outcomes will include (i) motivation to change PA and dietary intake as well as (ii) potential unintended health consequences (i.e. mental health and sleep duration). The motivational and mental health outcomes will be measured by in-app mini-surveys, whereas sleep duration will be measured by the wearable.

All primary and secondary outcome data will be collected at the baseline (i.e. pre-randomisation), at one month, three months, and at five months after the randomisation. The exploratory outcomes will be collected at the baseline and at five months after the randomisation.

The pre-planned primary analysis will compare the 2 physical activity outcomes and 4 dietary outcomes at five months post-randomisation between the control group and the three pooled financial incentives groups (i.e. being offered any level of financial incentive).

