- **Subgroup analyses:** Does the incentive scheme also work among specific population subgroups five months after randomisation in terms of improving dietary intake and PA (focusing on primary outcomes), comparing the behaviour of users allocated to a control group (no financial incentives offered) to the behaviour of users allocated to the pooled treatment groups (low, medium or high level of incentive offered)?
- Longer-term effects on motivation to change: Does offering financial incentives effectively increase participants' motivation to improve dietary intake and to increase PA level five months after randomisation, comparing the motivation level of users allocated to a control group (no financial incentives offered) to that of users allocated to the pooled treatment groups (low, medium or high level of incentive offered)?
- Unintended consequences: Does the incentive scheme have any significant impact on participants' sleep or mental health five months after randomisation, comparing the behaviour of users allocated to a control group (no financial incentives offered) to the behaviour of users allocated to the pooled treatment groups (low, medium or high level of incentive offered)?

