The degree of attrition might vary with outcome measures. As physical activity outcomes are passively captured by the wearable and require no extra burden from the users other than wearing the device and syncing it with the app, we expect the degree of attrition to be lower than for the dietary outcomes measured by Intake24, which require users to spend up to 20 minutes to complete each questionnaire. We will test for differing attrition rates separately for each type of primary outcome (we will use MVPA minutes for physical activity and fruit and vegetables for diet). If we find a ratio of attrition greater than 1.1 for a given primary outcome type, we will apply IPW for all corresponding primary and exploratory outcomes related to physical activity / diet as well.

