The impact of offering incentives (compared to not offering any incentives) on exploratory outcomes at the 5 months mark will be assessed using similar methods as the ones for the primary analysis. We will not impute values at baseline or at 5 months. If there are missing values for an exploratory outcome at baseline, we will add an indicator variable for missingness to the set of covariates so that all individuals with non-missing values for the outcome at 5 months can be included.

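### WHO-5, weight and sleep are scheduled at 1 and 3 months but compared between arms only at 5 months, when about 66% (pooled incentive) and 78% (control) are expected to be lost

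*Protocol*

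**What the plan says.** **Collection.** Section 2.3.3.2 makes mental well-being (WHO-5) and sleep duration the exploratory outcomes for unintended effects. For WHO-5 it says: "Mental wellbeing will be collected at baseline and key collection points (m1, m3, m5) by prompting users". Table 3 (section 2.3) agrees and shows sleep recorded by the wearable for the whole pilot. Weight is a secondary outcome. Section 2.3.2.3 includes it partly to assess obesity reduction and partly to "rule out potential unintended consequences on weight". On timing it says: "Participants will be asked to self-report their current weight at the baseline and each measurement timepoint".

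**Analysis.** The research question in section 2.1 concerns "sleep or mental health five months after randomisation". Section 2.6.3.10 says that "exploratory outcomes at the 5 months mark will be assessed using similar methods as the ones for the primary analysis". Section 2.6.3.6 sets the same single time point for secondary outcomes, hence for weight. Tables 3 and 11 agree. Section 2.6.3.7 runs the 1- and 3-month models for the six primary outcomes only.

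**Conflicting schedule.** The Executive Summary says: "The exploratory outcomes will be collected at the baseline and at five months after the randomisation". This does not fit Table 3 or section 2.3.3.2 for WHO-5.

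**Attrition weighting.** Section 2.6.3.1 triggers inverse probability weighting (IPW) when the control-to-incentive attrition ratio reaches 1.1. On its scope it says: "we will apply IPW for all corresponding primary and exploratory outcomes related to physical activity / diet as well".

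**Fallback.** Under Table 2 (section 2.2.3) and section 2.6.3.7, the main assessment moves to 3 months if the 5-month sample falls below 80% of 4,200.

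**The concern.** Suppose a participant's mood, sleep or weight worsens in the first weeks and they then leave. They may supply a 1-month value, but that value enters no pre-specified between-arm comparison. The planned comparison is made at the point of heaviest loss, where harm that leads to dropout is least visible.

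The planned weights do not solve this. Section 2.6.3.1 builds them from baseline variables, so they cannot recover a deterioration that begins after randomisation.

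What is at stake is how a null 5-month result on WHO-5, sleep or weight would be read. It would describe the minority who stayed but could be taken as evidence that the scheme had no unintended effects. The fallback adds a second problem: the primary outcomes could be judged at 3 months while these outcomes have no 3-month analysis specified.

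**Working it through.** **1. Reproduce the plan's attrition.** Table 6 gives approximate numbers randomised and numbers at 5 months. Attrition = 1 − N(5m)/N(randomised):

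- High: 1 − 700/1,900 = 63.2% (stated 62%)
- Medium: 1 − 700/1,950 = 64.1% (stated 63%)
- Low: 1 − 700/2,250 = 68.9% (stated 69%)
- Control: 1 − 2,100/9,400 = 77.7% (stated 78%)

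These agree with the printed rates, allowing for rounding of the Ns.

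**2. Pool the incentive arms**, as the planned comparison does. Randomised: 1,900 + 1,950 + 2,250 = 6,100.

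| Time | Incentive N | Control N | Incentive attrition | Control attrition | Ratio |
|---|---|---|---|---|---|
| 1m | 4,950 | 6,950 | 18.9% | 26.1% | 1.38 |
| 3m | 3,300 | 3,800 | 45.9% | 59.6% | 1.30 |
| 5m | 2,100 | 2,100 | 65.6% | 77.7% | 1.18 |

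All three ratios exceed 1.1, so the plan's own estimates predict that IPW will be triggered.

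**3. People seen at 1 month but not at 5.** If dropout is monotone: incentive 4,950 − 2,100 = 2,850; control 6,950 − 2,100 = 4,850. The total is 7,700 of 11,900, or 65%.

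**4. Fallback threshold.** 0.80 × 4,200 = 3,360. Neither place that describes the fallback says whether it reaches WHO-5, sleep or weight.

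**5. Precision, for illustration only.** With equal variances, SE is proportional to √(1/n₁ + 1/n₂).

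- 1m: √(1/4,950 + 1/6,950) = 0.0186
- 5m: √(2/2,100) = 0.0309
- Ratio: 0.60

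Use the ICC of 0.3 and baseline correlation of 0.5 from section 2.4.2.2. The household mix of 39/41/20% with 1, 2 and 3 adults gives a design effect of 1.335. Assume two-sided 5% and 80% power. The detectable difference is then about 0.052 SD at 1m, 0.067 SD at 3m and 0.087 SD at 5m. This shows the gain from larger numbers. It does not measure bias from dropout.

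**6. Which schedule is the outlier?** Table 3 and section 2.3.3.2 both place WHO-5 at 1 and 3 months. Table 2 also lists WHO-5, sleep and weight among the measures whose 3- and 5-month windows may be lengthened. The Executive Summary sentence stands alone. It does not affect weight, because the same summary collects secondary outcomes at every point.

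**The case against.** The choice of 5 months is explicit, consistent and matches the primary endpoint. Several stronger readings are tempting, and the document does not support them.

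- *Early harm is never looked at.* Table 13 provides dashboards by arm covering in-app survey results, BMI and monthly sleep change. Section 2.7.2 sets up a clinical safety group and a safety officer, and section 2.7.1 an ad hoc DMC with unblinded access. Tables 20 and 21 plan 12 interviews and a four-person focus group with dropouts. What stands is narrower. The dashboards are descriptive, the DMC meets only when called, and the 16 dropouts (four per arm) are seen after the intervention ends. None is a pre-specified quantitative comparison.
- *Benefit is tested at three times and harm at one.* The line falls between primary and other outcomes. Energy expenditure, energy intake, the healthy eating score and motivation are also tested only at 5 months, as is the main benefit comparison.
- *These are purely harm outcomes.* WHO-5 and sleep are framed as able to move either way, and weight is secondary with obesity reduction named first.
- *The 1- and 3-month WHO-5 data would not exist.* One summary sentence against three other places makes that unlikely. It is a conflict to reconcile.
- *These outcomes will be left unweighted.* Section 2.6.3.1 does not name them, but sections 2.6.3.6 and 2.6.3.10 promise methods similar to the primary analysis. The text is ambiguous; it does not exclude them.
- *The attrition figures are themselves a sign of harm.* The plan expects more loss in control because those users have less incentive to stay. That says nothing about harm from incentives.

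**Conclusion.** The point holds as a cheap improvement to what the trial can conclude, together with one internal contradiction to correct. The protocol schedules WHO-5 and weight at 1 and 3 months and sleep throughout. It fixes their only pre-specified between-arm comparison at 5 months, when expected attrition is about 66% and 78%, against 19% and 26% at 1 month. A null 5-month result would offer limited reassurance, and the fallback would leave these outcomes without a matching 3-month analysis.

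This rests on the Table 6 counts, which are general estimates. WHO-5 is optional at baseline, so its numbers may be lower. The 66% is a pooled figure derived here; by single arm the printed range is 62% to 78%. The 65% in step 3 assumes monotone dropout, and the detectable differences assume a two-sided 5% level. The document gives no evidence that early harm will occur or will drive dropout. The point is that the planned analysis is poorly placed to show it if it does.

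**What to change.** 1. In Tables 3 and 11, and in sections 2.6.3.6 and 2.6.3.10, analyse WHO-5, sleep and weight at 1, 3 and 5 months with the same pooled-versus-control model. Label the 1- and 3-month results exploratory.
2. Reconcile the Executive Summary sentence on exploratory outcomes with Table 3 and section 2.3.3.2.
3. In section 2.6.3.1, state that IPW, when triggered, also applies to these three outcomes.

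Item 1 also closes the gap under the 3-month fallback.

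The cost is six further comparisons (three outcomes at two time points) on data already scheduled, plus wording. The downside is some chance signals among exploratory results, which the label should make plain. Adding the earlier time points reduces the dependence on those who stayed but does not remove dropout bias.

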2.4 Sample size and minimum detectable size

2.4.1 Summary

The trial will adopt **a household-level randomisation**, with a target sample size of **around 4,200 participants** (2,100 in the control arm, 700 per intervention arm) at the final data collection point (**5 months after the randomisation**) to be powered to detect effect sizes deemed substantive from previous literature (see Section 2.4.2.2 Table 5). We expect users to come from ~2,300 households based on the demographic profile of Wolverhampton LA (see Appendix B).

To achieve a post-attrition sample of 4,200 participants, HUL expects to recruit a sample of around **25,800 participants** at the beginning of the baseline stage, given the attrition rate at various trial stages estimated by HUL (see Section 2.4.2.3 Table 6).

BIT has conducted power calculations for the primary research question "Does the incentive scheme improve physical activity (PA) and diet at the five month mark?". The power calculations focus on the primary outcomes. The primary analysis pools all the treatment arms together and assesses their overall difference against the control.

Given the post-attrition sample size of 4,200 participants, the minimum effect sizes we are powered (at 80% level) to detect at the 5-month's mark in the primary analysis are:

Physical activity primary outcomes:

- Daily MVPA (min/day): 2.4 min/day
- Daily steps: 371 steps/day

Dietary primary outcomes:

- Fruit and vegetables (g/day): 18.7 g/day
- Fibre (g/day): 0.74 g/day
- Free sugars (% food energy): 0.63%
- Saturated Fat (% food energy): 0.31%

The following subsections provide details on the key assumptions and decisions made concerning the power calculation. First, we provide the minimum required sample size at the analysis stage (post-attrition) given the target effect sizes for the primary outcomes (see Table 5). Then, we show the minimum required sample size at the recruitment stage (pre-attrition) given the predicted attrition rate at various stages (see Table 6) based on HUL's estimations. Last, we calculate the minimum detectable effect size for primary outcomes (see Table 7) based on the target sample size confirmed as feasible for this project by HUL and DHSC.

For further information on specific assumptions behind household-level randomisation, multiple-comparisons-adjustment, inclusion of covariates, and allocation ratio among trial arms, please see Appendix B.

